The endpoint of this Project will be to analyze 30 positive ROS1 and 120 positive ALK samples to validate the diagnostic method.

Given an estimated prevalence of ROS1 at 1-2% and ALK at 3-5% for NSCLC, an initial set of 1000 patients will be screened. An interim analysis will be performed at the first 1000 NSCLC samples to evaluate prevalence rates (tentatively 10 ROS1+ and 40 ALK+).

For the majority of molecular tests, it is expected that at least 50 positive patient samples be utilized for validation, and ideally at least 10 positives representing each variant being detected¹. Given the low prevalence of ROS1 which has 16 unique variants and recent analysis demonstrating that in 30 ROS1+ patient samples, there is representation of the 3 dominant variants suitable for analytical validation², it is necessary to screen at least 3000 NSCLC samples for identifying positive samples for both ROS1 and ALK that should be sufficient for analytical validation of the NGS platform. If anticipated prevalence rates at the 3000 sample mark do not align with determined prevalence rates at this stage and/or 30 positive ROS1 and 120 positive ALK samples are not obtained, an additional 3000 patients will be screened for a potential total of 6000 patients. The overall screening will occur at 3 or more sites. Patients will only participate in the study for the initial sample collection period.

The study will be completed in approximately 48 months.

Study Treatment

None.

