7.4 Study size

The results regarding the presence or absence of specific gene fusions (ALK and/or ROS1) after applying NGS will be confirmed using certified and validated test for clinical use, which will allow the specificity of NGS test for the analyzed gene. In all participant subjects the presence of gene ALK and ROS1 variation will be analyzed which will allow to estimate the sensitivity in the NGS test.

The specificity of the NGS trial will be calculated based on cases with a particular gene fusion where a result has been obtained through a certified test. Thus, the specificity will be equal to the confirmed cases through certified test divided by the total of NGS identified mutated cases number. The sensitivity will be calculated dividing the number of cases with a confirmed gene fusion by an ALK and/or ROS1 certified test by the number of the same cases in which the fusion was identified by NGS.

The gene fusion in ROS1 has been selected as the primary variation for the statistical analysis plan, since is the less frequent variation in lung cancer (COSMIC Sanger Database) with a prevalence of 1-2%. The confidence intervals for sensitivity and specificity will be calculated according to the efficiency method of the marker (efficient score method, Newcombe, 1998, Wilson, 1927).^{19, 20}

This study expects to analyze a total of 30 tumors with alterations in the ROS1 gene and 120 alterations in ALK. Thus, for a precision up to 80% (either specificity or sensitivity), will be enough information to establish a sensitivity and specificity estimation of the NGS trial within 0.1 points and 0.05 points (wide of 95% of the confidence interval) respectively.

Given an estimated prevalence of ROS1 at 1-2% and ALK at 3-5% for NSCLC, an initial set of 1000 patients will be screened.

An interim analysis will be performed at the first 1000 NSCLC samples to evaluate prevalence rates. If anticipated prevalence rates do not align with determined prevalence rates at this stage, an additional 2000 patients will be screened for a potential total of 3000 patients.

A subsequent interim analysis will be performed at the 3000 NSCLC samples to evaluate prevalence rates. If anticipated prevalence rates do not align with

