8 STATISTICAL METHODOLOGY AND STATISTICAL ANALYSES

8.1 STATISTICAL METHODS

a. Sample Size Calculation:

The sample size can be estimated according to a desired sensitivity or specificity, and the choice of the N obtained will be defined by privileging to maximize the sensitivity (cut-off value defined > 0.8). The sample size necessary to demonstrate hypothesis will be defined. This calculation will be made at each of the interim analysis, to evaluate the total number of patients to be recruited. The sample size calculation formulas are defined

Formula of the sample size calculation dependent on Sensitivity

$$N(sN) = \frac{TP+FN}{P}$$

Where,

$$TP+FN = z^2 \times \frac{(SN(1-SN))}{W^2}$$

TP : Prevalence of ALK rearrangements in the population and / or in the data set of the interim analysis.

SN : Minimal acceptable sensitivity

W : Desired confidence interval, also called α (here a 99 % is desired)

z : Constant dependent on the desired confidence interval, this value is obtained from the table of the normal distribution. For a 95 % confidence interval the value of z is 1.96, and for a range of 99 %, it is 2.58.

i. Formula of the calculation of the sample size dependent on the Specificity:

$$N(sP) = \frac{FP+TN}{(1-P)}$$

Where,

$$FP+TN = z^2 \times \frac{(SP(1-SP))}{W^2}$$

P : Prevalence of ALK rearrangements in the population and / or in the data set of the interim analysis.

SP : Minimal acceptable specificity

W : Desired confidence interval, also called α (here a 99 % is desired)

z : Constant dependent on the desired confidence interval, this value is obtained from the table of the normal distribution. For a 95 % confidence interval the value of z is 1.96, and for a range of 99 %, it is 2.58

b. Concordance test:

i. Test type:

The agreement between Ventana ALK and NGS assay for ALK will be evaluated based on the Binary Qualitative type (Two tails), where the results can only have two values (concordance, discordance). The following metrics will be evaluated from the results:

- *Sensitivity:* $\frac{TP}{(TP+FN)}$
- *Specificity:* $\frac{TN}{(TN+FP)}$

- *Precision: PPV* = $\frac{TP}{(TP+FP)}$
- *Accuracy*: $\frac{TP+TN}{TP+TN+FP+FN}$
- Limit of detection (LOD): They will be established a priori by the reference values delivered by Thermo Fisher. After the interim analysis, these will be re-evaluated and / or modified. Among the influential values in the limits of detection are: the coverage

ii. Concordance methods:

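### 30 ROS1-positive and 120 ALK-positive tumours do not give the stated 95% precision of 0.1 and 0.05 at 80%; the Wilson half-widths are 0.14 and 0.07

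*Protocol*

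**What the plan says.** Protocol section 7.4 (Study size) sets the counts: "This study expects to analyze a total of 30 tumors with alterations in the ROS1 gene and 120 alterations in ALK". The Abstract, under Study Design, makes the same counts the goal of the project: "The endpoint of this Project will be to analyze 30 positive ROS1 and 120 positive ALK samples to validate the diagnostic method". It adds that a further 3000 patients will be screened if they are not reached at 3000.

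Section 7.4 then states the precision these counts are meant to deliver. The planning value is given in the phrase "for a precision up to 80% (either specificity or sensitivity", and the result is said to be "within 0.1 points and 0.05 points (wide of 95% of the confidence interval) respectively". For the interval, the section says "The confidence intervals for sensitivity and specificity will be calculated according to the efficiency method of the marker" and cites the score-method papers, that is, the Wilson interval. It also says: "The gene fusion in ROS1 has been selected as the primary variation for the statistical analysis plan".

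Specificity is defined there in an unusual way: "the specificity will be equal to the confirmed cases through certified test divided by the total of NGS identified mutated cases number". Its denominator is therefore the NGS-positive cases.

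SAP section 8.1 gives a generic sample-size formula and a sensitivity threshold ("cut-off value defined > 0.8"). It neither repeats nor corrects the 0.1 and 0.05.

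**The concern.** The counts, the planning value, the interval method and the confidence level all stand in one section, so the precision can be recomputed without any outside figure. A binomial proportion of 0.80 on 30 observations has a standard error of 0.073, so a 95% margin of 0.10 is not plausible on sight.

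This sentence is the only precision argument offered for the 30 and 120 targets, and under the Abstract those targets help decide whether screening goes on. A study that stopped at exactly those counts, with 80% observed, would report intervals about 40% wider than the protocol promises. For ROS1 the interval would reach down to 63%, well below the 0.8 that the SAP uses as its sensitivity threshold.

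**Working it through.** **Inputs (Protocol 7.4).** n = 30 (ROS1) and 120 (ALK); p = 0.80; two-sided 95%, z = 1.96; Wilson score interval.

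**Formula.**
- Centre = (p + z²/2n) / (1 + z²/n)
- Half-width = z·√[p(1−p)/n + z²/4n²] / (1 + z²/n)

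**n = 30.**
- Centre = (0.80 + 0.0640)/1.1280 = 0.766
- Half-width = 1.96 × √(0.005333 + 0.001067)/1.1280 = 0.139
- Interval 0.627 to 0.905, full width 0.278

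**n = 120.**
- Centre = (0.80 + 0.0160)/1.0320 = 0.791
- Half-width = 1.96 × √(0.001333 + 0.0000667)/1.0320 = 0.071
- Interval 0.720 to 0.862, full width 0.142

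**Attempt to reproduce 0.1 and 0.05.** No 95% method tried reaches them at 80%:

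| Method (half-width) | n = 30 | n = 120 |
|---|---|---|
| Stated | 0.10 | 0.05 |
| Wilson | 0.139 | 0.071 |
| Wald | 0.143 | 0.072 |
| Wilson, continuity-corrected | 0.154 | 0.075 |
| Clopper-Pearson | 0.154 | 0.075 |

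Pooling all 150 positives gives 0.064 (Wilson), still above 0.05.

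By the normal approximation the stated figures imply z = 0.10/√(0.16/30) = 0.05/√(0.16/120) = 1.37, which is about 83% confidence. Both figures imply the same z because 0.1/0.05 = 2 = √(120/30). This also suggests that they were meant as ROS1 then ALK.

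**Sensitivity to the planning value (Wilson half-widths).**

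| p | n = 30 | n = 120 |
|---|---|---|
| 0.50 | 0.168 | 0.088 |
| 0.80 | 0.139 | 0.071 |
| 0.85 | 0.127 | 0.064 |
| 0.90 | 0.111 | 0.054 |
| 0.95 | 0.089 | 0.041 |

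The stated half-widths are met only from p of about 0.93 (n = 30) and 0.92 (n = 120). Reading the 80% as an upper bound makes matters worse.

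**Reading the pair as sensitivity then specificity.**
- ROS1 sensitivity on 30 positives has half-width 0.139, which misses 0.10.
- Specificity as section 7.4 defines it rests on NGS-positive cases, so on roughly 30 or 120 if the two tests largely agree. It misses 0.05 for both genes (0.139 and 0.071).
- ALK meets both figures only if specificity is taken over test-negative patients. Assuming 4% prevalence among 3000, that is 3000 × 0.96 = 2,880 patients, with half-width 0.015.

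**Positives needed at 80%.** The smallest n with a Wilson half-width of at most 0.10 is 60, and of at most 0.05 is 245. The SAP 8.1 formula z²·SN(1−SN)/W² gives 3.84 × 0.16/0.01 = 61.5 and 3.84 × 0.16/0.0025 = 245.9, that is 62 and 246.

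**The case against.** The arithmetic at 80% is hard to contest, so the case on the other side concerns reading and consequence.

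- **Grammar.** The nearest pair before the figures is sensitivity and specificity. With the SAP's TN/(TN+FP), ALK then meets both figures (0.071 and about 0.015). This is fair for ALK. It does not rescue ROS1, and it replaces section 7.4's own definition of specificity.
- **Other grounds for the counts.** The Abstract also supports the numbers by a general expectation of at least 50 positives, ideally 10 per variant, and by 30 ROS1-positive samples covering the three dominant variants. That stands: the counts do not rest on precision alone. Moreover, the extension rule in section 7.4 depends on prevalence; only the Abstract ties it to reaching 30 and 120.
- **The SAP has moved on.** It recalculates sample size at each interim analysis, lists re-assessments whose content is not shown, and tests concordance for ALK only. The practical weight of the ROS1 figure is therefore smaller than section 7.4 suggests. But the SAP supplies no replacement precision figure, and the supplied protocol still carries the claim.
- **Conditional effect.** The excess of about 40% applies at 80% and at exactly 30 and 120 positives. More positives or higher agreement would narrow the intervals. That is true, but 80% is the protocol's own planning value.

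These points limit the consequences. None makes the sentence correct.

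**Conclusion.** The concern holds. On the more lenient half-width reading, the 95% precision at 80% is 0.139 instead of 0.10 for 30 positives (39% wider) and 0.071 instead of 0.05 for 120 (42% wider). Read literally as full width, the values are about 2.8 times those stated. The ROS1 figure fails on every reading at 80%. The ALK figure fails unless the pair means sensitivity then specificity and a conventional specificity denominator is substituted. The conclusion rests only on section 7.4's own inputs: 30 and 120 positives, 80%, 95% and the Wilson interval. It would change if the protocol assumed true agreement of about 93% (ROS1) and 92% (ALK) or more, but no such assumption is stated.

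**What to change.** Replace the precision sentence in Protocol 7.4 with wording such as: *With 30 ROS1-positive and 120 ALK-positive tumours and an observed proportion of 80%, the 95% Wilson intervals are 0.63 to 0.90 (half-width 0.14) and 0.72 to 0.86 (half-width 0.07).* State separately the precision for specificity and name its denominator. Over test-negative patients it is about 0.015 at 80% with roughly 2,900 negatives.

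If 0.10 and 0.05 are to be kept, say that they are half-widths at 80% and need about 60 ROS1-positive and 245 ALK-positive tumours. The planned cap of 6000 yields 60 to 120 ROS1 positives at 1–2% prevalence, so 0.10 is within reach. For ALK it yields 180 to 300 at 3–5%: the half-width is 0.058 with 180, 0.0504 with 240 (4%) and 0.045 with 300. Thus 0.05 needs an ALK prevalence of at least 245/6000 = 4.1%, and the protocol should say so.

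The cost is protocol wording and a less favourable stated precision. The correction itself needs no extra patients. Keeping 0.10 and 0.05 would mean screening beyond the point where 30 and 120 are reached, though for ALK prevalence of about 4.1% or more it stays within the existing cap.

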7.5 Data management

As used in this protocol, the term case report form (CRF) should be understood to refer to either a paper form or an electronic data record or both, depending on the data collection method used in this study.

A CRF is required and should be completed for each included subject. The completed original CRFs are the sole property of Pfizer and should not be made available in any form to third parties, except for authorized representatives of Pfizer or appropriate regulatory authorities, without written permission from Pfizer.

The investigator has ultimate responsibility for the collection and reporting of all clinical, safety and laboratory data entered on the CRFs and any other data collection forms (source documents) and ensuring that they are accurate, authentic / original, attributable, complete, consistent, legible, timely (contemporaneous), enduring and available when required.

The CRFs must be signed by the investigator or by an authorized staff member to attest that the data contained on the CRFs is true. Any corrections to entries made in the CRFs, source documents must be dated, initialed and explained (if necessary) and should not obscure the original entry."

In most cases, the source documents are the hospitals or the physician's subject chart. In these cases data collected on the CRFs must match the data in those charts.

In some cases, the CRF, or part of the CRF, may also serve as source documents. In these cases, a document should be available at the investigator's site as well as at Pfizer and clearly identify those data that will be recorded in the CRF, and for which the CRF will stand as the source document.

7.6 Data analysis

Detailed methodology for summary and statistical analyses of data collected in this study will be documented in a Statistical Analysis Plan (SAP), which will be dated, filed and maintained by the sponsor.

The SAP may modify the plans outlined in the protocol; any major modifications of primary endpoint definitions or their analyses would be reflected in a protocol amendment.

7.7 Quality control

During study conduct, Pfizer or its agent will conduct periodic monitoring visits to ensure that the protocol and GCPs are being followed. The monitors may review source documents to confirm that the data recorded on CRFs is accurate.

The investigator and institution will allow Pfizer monitors or its agents and appropriate regulatory authorities direct access to source documents to perform this verification.

The study site may be subject to review by the Institutional Review Board (IRB)/Independent Ethics Committee (IEC), and/or to quality assurance audits performed by Pfizer, or companies working with or on behalf of Pfizer, and/or to inspection by appropriate regulatory authorities.

It is important that the investigator(s) and their relevant personnel are available during the monitoring visits and possible audits or inspections and that sufficient time is devoted to the process.

7.8 Record Retention

To enable evaluations and/or audits from regulatory authorities or Pfizer, the investigator agrees to keep records, including the identity of all participating subjects (sufficient information to link records, e.g., CRFs and hospital records), all original signed informed consent forms, copies of all CRFs, source documents, and detailed records of treatment disposition, and adequate documentation of relevant correspondence (e.g., letters, meeting minutes, telephone calls reports).

The records should be retained by the investigator according to ICH, local regulations, or as specified in the Clinical Study Agreement, whichever is longer.

If the investigator becomes unable for any reason to continue to retain study records for the required period (e.g., retirement, relocation), Pfizer should be prospectively notified. The study records must be transferred to a designee acceptable to Pfizer, such as another investigator, another institution, or to an independent third party arranged by Pfizer. The investigator must obtain Pfizer's written permission before disposing of any records, even if retention requirements have been met.

7.9 Other aspects

Not applicable.

8 PROTECTION OF HUMAN SUBJECTS

8.1 Patient Information and Consent

All parties will ensure protection of patient personal data and will not include patient names on any sponsor forms, reports, publications, or in any other disclosures, except where required by laws. In case of data transfer, Pfizer will maintain high standards of confidentiality and protection of patient personal data.

The informed consent form must be in compliance with local regulatory requirements and legal requirements.

The informed consent form used in this study, and any changes made during the course of the study, must be prospectively approved by both the IRB/IEC and Pfizer before use.

The investigator must ensure that each study patient, or his/her legally acceptable representative, is fully informed about the nature and objectives of the study and possible risks associated with participation.

The investigator, or a person designated by the investigator, will obtain written informed consent from each patient or the patient's legally acceptable representative before any study-specific activity is performed. The investigator will retain the original of each patient's signed consent form and one copy will be given to the patient or his/her representative.

8.2 Patient withdrawal

Patients may be withdrawn at any time at the discretion of the investigator or sponsor for safety, behavioral, or administrative reasons. In any circumstance, every effort should be made to document subject outcome, if possible. The investigator should inquire about the reason for withdrawal and follow-up with the subject regarding any unresolved adverse events.

If the patient withdraws from the study, and also withdraws consent for disclosure of future information, no further evaluations should be performed, and no additional data should be collected. The sponsor may retain and continue to use any data collected if no withdrawal of consent is requested.

8.3 Institutional Review Board (IRB)/Independent Ethics Committee (IEC)

It is the responsibility of the investigator to have prospective approval of the study protocol, protocol amendments, and informed consent forms, and other relevant documents, (e.g., recruitment advertisements), if applicable, from the IRB/IEC.

All correspondence with the IRB/IEC should be retained in the Investigator File. Copies of IRB/IEC approvals should be forwarded to Pfizer.

8.4 Ethical Conduct of the Study

The study will be conducted in accordance with legal and regulatory requirements, as well as the general principles set forth in the International Ethical Guidelines for Biomedical Research Involving Human Subjects (Council for International Organizations of Medical Sciences 2002), Guidelines for Good Clinical Practice (International Conference on Harmonization 1996), and the Declaration of Helsinki (World Medical Association 2008).

In addition, the study will be conducted in accordance with the protocol, the International Conference on Harmonization guideline on Good Clinical Practice, and applicable local regulatory requirements and laws.

9 PUBLICATION OF STUDY RESULTS

Since the objective of Pfizer's Center of Excellence is to lead the research in precision Medicine, publications with Study Researchers will be promoted, whether or not the results are favorable to the study.

Since the Study is part of a multi-center study, Study Researchers agree that publications are to be a joint publications, even after the study is finished.

To ensure against inadvertent disclosure of Confidential Information or unprotected Inventions, Study Researchers will provide Pfizer an opportunity to review any proposed joint publication or other type of disclosure before it is submitted or otherwise disclosed.

Study Researchers will provide manuscripts, abstracts, or the full text of any other intended disclosure (poster presentation, invited speaker or guest lecturer presentation, etc.) to Pfizer at least 60 days before they are submitted for publication or otherwise disclosed.

Study Researchers will, on request, remove any previously undisclosed Confidential Information (other than the Study results themselves) before disclosure.

For all publications relating to the Study, the Center of Excellence will comply with recognized ethical standards concerning publications and authorship, including Section II - "Ethical Considerations in the Conduct and Reporting of Research" of the Uniform Requirements for Manuscripts Submitted to Biomedical Journals, <http://www.icmje.org/index.html#authorship>, established by the International Committee of Medical Journal Editors.

APPENDIX 1. LIST OF STAND ALONE DOCUMENTS.

Document reference	Title
OCP Fusion including DNA/RNA extraction	NGS SOP for FFPE processing
Streck cell free RNA BCT	Blood (RNA) tube collection and storage
Streck cell free DNA BCT	Blood (DNA) tube collection and storage

1 AMENDMENTS FROM PREVIOUS VERSION(S)

Version	Effective Date	Change Type (New, Revise, Admin)	Summary of Revisions
2.0	10-Jul-2019	Admin	New version signed to recover e-copy. Minor text revision included.
1.0	15-May-2018	Admin	Document signed and attached appendix 3 to 8.
1.0	05-Sep-2016	New	New Document.

2 INTRODUCTION

Note: in this document any text taken directly from the Non-Interventional (NI) study protocol is *italicised*.

Non-small cell lung cancer (NSCLC) is a common cause of cancer mortality throughout the world. In 2007, there were 1.5 million new lung cancer cases diagnosed worldwide, including around 733,100 cases in the South American Region.⁶

Approximately 85% of lung cancer is histologically defined as non small cell and the remaining 14% as small cell. The majority of patients with NSCLC present with inoperable locally advanced (Stage IIIB) or metastatic (Stage IV) disease for which no curative treatment is yet available. ^{7, 8, 9, 10, 11, 12}

The rapid and efficient identification of key driver genes in non-small-cell lung cancer (NSCLC) is becoming increasingly important.¹⁷ Clinical screening efforts have revealed that the most common mutations in lung cancer specimens involve EGFR and KRAS, along with 10 other genes that show a prevalence of mutation in 5% or less of tumors. The ALK gene is rearranged in around 3%-5% of patients with NSCLC and has been the focus of intense basic and clinical research, suggesting that the frequency of the gene rearrangement is similar in Asian and Western patients.

ROS1 is a receptor tyrosine kinase of the insulin receptor family. Chromosomal rearrangements involving the ROS1 gene were originally described in.¹⁶ More recently, ROS1 fusions were identified as potential driver mutations in an NSCLC cell line (HCC78; SLC34A2-ROS1) and an NSCLC patient sample (CD74-ROS1).¹⁸ These fusions led to constitutive kinase activity and were associated with sensitivity in vitro and in vivo to crizotinib.

The identification of these and other genes has challenged the current state of the art in molecular pathology from single genes test to multiplexed assays. The Ion Torrent OncoPrint™ Focus Assay is a multi-biomarker next generation sequencing designed for nucleic acid extracted from Formalin Fixed Paraffin Embedded (FFPE) tissue. The assay detects multiples types of variants in 52 solid tumor genes analyzing simultaneously DNA and RNA.

[figure not shown]
The methods describe here apply to N° X9001083 clinical study protocol Non-Interventional Multi-Center Study for Molecular Diagnostic Technologies Validation in NSCLC Patients.

The objective of this study is to determine concordance between the Vysis ALK Break Apart FISH test or the Ventana ALK IHC test and ThermoFisher NGS technology
 This statistical analysis plan (SAP) is, in general, consistent with the Statistical Methodology section of NIRVANA Protocol and includes additional details of data summaries and data presentations to be presented in the clinical study report (CSR). Details of the changes in statistical methods between the protocol and the SAP are provided in Section.

